3.6 CRITERIA FOR REMOVAL FROM PROTOCOL THERAPY AND OFF STUDY CRITERIA

Prior to removal from study, effort must be made to have all subjects complete a safety visit approximately 30 days following the last dose of study therapy

3.6.1 Criteria for Removal from Protocol Therapy

Treatment may continue until one of the following criteria applies:

- Disease progression (per immune-related response criteria).
- Intercurrent illness that prevents further administration of treatment
- Unacceptable toxicity as defined in section **3.4**
- Participant requests to be withdrawn from active therapy
- General or specific changes in the patient's condition render the patient unacceptable for further treatment in the judgment of the investigator
- Delayed recovery from toxicity that prevents re-treatment in ≤ 28 days of scheduled therapy
- Investigator discretion
- Positive pregnancy test

3.6.2 Off-Study Criteria

- Participant requests to be withdrawn from study
- Investigator discretion
- Death
- PI decision to end the study

3.6.3 Off-Study Procedure

Authorized staff must notify Central Registration Office (CRO) when a subject is taken off protocol therapy and when a subject is taken off-study. A Participant Status Updates Form from the web site (<http://home.ccr.cancer.gov/intra/eligibility/welcome.htm>) main page must be completed and sent via encrypted email to: NCI Central Registration Office [contact].

4 CONCOMITANT MEDICATIONS/MEASURES

All routine and appropriate supportive care (including blood products) will be provided during this study, as clinically indicated, and in accordance with the standard of care practices. Clinical judgment should be utilized in the treatment of any AE experienced by the patient.

Information on all concomitant medications, administered blood products, as well as interventions occurring during the study must be recorded on the patient's eCRF.

4.1 SUPPORTIVE CARE GUIDELINES

Subjects should receive appropriate supportive care measures as deemed necessary by the treating investigator. Suggested supportive care measures for the management of adverse events with potential immunologic etiology are outlined below. Where appropriate, these guidelines include the use of oral or intravenous treatment with corticosteroids as well as additional anti-inflammatory agents if symptoms do not improve with administration of corticosteroids. Note that several courses of steroid tapering may be necessary as symptoms may worsen when the steroid dose is decreased. For each disorder, attempts should be made to rule out other causes such as metastatic disease or bacterial or viral infection, which might require additional supportive care. The treatment guidelines are intended to be applied when the investigator determines the events to be related to pembrolizumab.

Note: if after the evaluation the event is determined not to be related, the investigator does not need to follow the treatment guidance (as outlined below).

It may be necessary to perform conditional procedures such as bronchoscopy, endoscopy, or skin photography as part of evaluation of the event.

4.1.1 Pneumonitis:

- For Grade 2 events, treat with systemic corticosteroids. When symptoms improve to Grade 1 or less, steroid taper should be started and continued over no less than 4 weeks.
- For Grade 3-4 events, immediately treat with intravenous steroids. Administer additional anti-inflammatory measures, as needed.
- Add prophylactic antibiotics for opportunistic infections in the case of prolonged steroid administration.

4.1.2 Diarrhea/Colitis

- Subjects should be carefully monitored for signs and symptoms of enterocolitis (such as diarrhea, abdominal pain, blood or mucus in stool, with or without fever) and of bowel perforation (such as peritoneal signs and ileus).
- All subjects who experience diarrhea/colitis should be advised to drink liberal quantities of clear fluids. If sufficient oral fluid intake is not feasible, fluid and electrolytes should

be substituted via IV infusion. For Grade 2 or higher diarrhea, consider GI consultation and endoscopy to confirm or rule out colitis.

- For Grade 2 diarrhea/colitis, administer oral corticosteroids.
- For Grade 3 or 4 diarrhea/colitis, treat with intravenous steroids followed by high dose oral steroids.
- When symptoms improve to Grade 1 or less, steroid taper should be started and continued over no less than 4 weeks.

4.1.3 Type 1 diabetes mellitus

- (if new onset, including diabetic ketoacidosis [DKA]) or \geq Grade 3 Hyperglycemia, if associated with ketosis (ketonuria) or metabolic acidosis (DKA)
- For T1DM or Grade 3-4 Hyperglycemia
- Insulin replacement therapy is recommended for Type I diabetes mellitus and for Grade 3-4 hyperglycemia associated with metabolic acidosis or ketonuria.
- Evaluate patients with serum glucose and a metabolic panel, urine ketones, glycosylated hemoglobin, and C-peptide.

4.1.4 Hypophysitis

- For Grade 2 events, treat with corticosteroids. When symptoms improve to Grade 1 or less, steroid taper should be started and continued over no less than 4 weeks. Replacement of appropriate hormones may be required as the steroid dose is tapered.
- For Grade 3-4 events, treat with an initial dose of IV corticosteroids followed by oral corticosteroids. When symptoms improve to Grade 1 or less, steroid taper should be started and continued over no less than 4 weeks. Replacement of appropriate hormones may be required as the steroid dose is tapered.
- Hyperthyroidism or Hypothyroidism
- Thyroid disorders can occur at any time during treatment. Monitor patients for changes in thyroid function (at the start of treatment, periodically during treatment, and as indicated based on clinical evaluation) and for clinical signs and symptoms of thyroid disorders.
- Grade 2 hyperthyroidism events (and Grade 2-4 hypothyroidism)
 - In hyperthyroidism, non-selective beta-blockers (e.g. propranolol) are suggested as initial therapy.
 - In hypothyroidism, thyroid hormone replacement therapy, with levothyroxine or liothyronine, is indicated per standard of care.

4.1.4.1 Grade 3-4 hyperthyroidism

Treat with an initial dose of IV corticosteroid followed by oral corticosteroids. When symptoms improve to Grade 1 or less, steroid taper should be started and continued over no less than 4 weeks. Replacement of appropriate hormones may be required as the steroid dose is tapered.

4.1.5 Hepatic

- For Grade 2 events, monitor liver function tests more frequently until returned to baseline values (consider weekly).

Treat with IV or oral corticosteroids

- For Grade 3-4 events, treat with intravenous corticosteroids for 24 to 48 hours.
- When symptoms improve to Grade 1 or less, a steroid taper should be started and continued over no less than 4 weeks.

4.1.6 Renal Failure or Nephritis

- For Grade 2 events, treat with corticosteroids.
- For Grade 3-4 events, treat with systemic corticosteroids.
- When symptoms improve to Grade 1 or less, steroid taper should be started and continued over no less than 4 weeks.

Management of Infusion Reactions: Signs and symptoms usually develop during or shortly after drug infusion and generally resolve completely within 24 hours of completion of infusion.

Table 2 below shows treatment guidelines for subjects who experience an infusion reaction associated with administration of pembrolizumab (MK-3475).

Table 2: Treatment guidelines for those who experience infusion reaction associated with pembrolizumab.

NCI CTCAE Grade	Treatment	Premedication at subsequent dosing
Grade 1 Mild reaction; infusion interruption not indicated; intervention not indicated	Increase monitoring of vital signs as medically indicated until the subject is deemed medically stable in the opinion of the investigator.	None
Grade 2 Requires infusion interruption but responds promptly to symptomatic treatment (e.g., antihistamines, NSAIDS, narcotics, IV fluids); prophylactic medications indicated for <=24 hrs.	Stop Infusion and monitor symptoms. Additional appropriate medical therapy may include but is not limited to: IV fluids Antihistamines NSAIDS Acetaminophen Narcotics Increase monitoring of vital signs as medically indicated until the subject is deemed medically stable in the opinion of the investigator. If symptoms resolve within one hour of stopping drug infusion, the infusion may be restarted at 50% of the original infusion rate	Subject may be pre-medicated 1.5h (\pm 30 minutes) prior to infusion of pembrolizumab (MK-3475) with: Diphenhydramine 50 mg po (or equivalent dose of antihistamine). Acetaminophen 500-1000 mg PO (or equivalent dose of antipyretic).

NCI CTCAE Grade	Treatment	Premedication at subsequent dosing
	
(e.g., from 100 mL/hr. to 50 mL/hr.). Otherwise dosing will be held until symptoms resolve and the subject should be pre-medicated for the next scheduled dose.
 
Subjects who develop Grade 2 toxicity despite adequate premedication should be permanently discontinued from further trial treatment administration.
	
Grades 3 or 4 Grade 3: Prolonged (i.e., not rapidly responsive to symptomatic medication and/or brief interruption of infusion); recurrence of symptoms following initial improvement; hospitalization indicated for other clinical sequelae (e.g., renal impairment, pulmonary infiltrates) Grade 4: Life-threatening; pressor or ventilatory support indicated	
Stop Infusion.
 
Additional appropriate medical therapy may include but is not limited to:
 
IV fluids Antihistamines NSAIDS Acetaminophen Narcotics Oxygen Pressors Corticosteroids Epinephrine
 
Increase monitoring of vital signs as medically indicated until the subject is deemed medically stable in the opinion of the investigator.
 
Hospitalization may be indicated.
 
Subject is permanently discontinued from further trial treatment administration.
	No subsequent dosing
Appropriate resuscitation equipment should be available in the room and a physician readily available during the period of drug administration.		

5 BIOSPECIMEN COLLECTION

5.1 CORRELATIVE STUDIES FOR RESEARCH

The correlative studies which we wish to perform are outlined below and summarized in the table. A description of each test including a brief statement of rationale and processing information is made below.

Test/assay	Volume blood (approx.)	Type of tube	Collection point (+/- 48hrs)	Location of specimen analysis ²
Immune- monitoring	120mls (for PBMC)	EDTA	See Study Calendar 3.5	[name] Lab
	5-10mls (for serum)	EDTA		
Immune cell infiltration (e.g. CD3+ CD4/8 cells etc.) as well as other surface markers such as PD-L1.	Optional tumor biopsy	NA	Baseline and Cycle 3 Day 1 +/- 7 days	[name] Lab
RNA Nanostring analysis (nCounterPan Cancer Immunology Profile)	Optional tumor biopsy		Cycle 3 Day 1 +/- 7 days	[name] Lab
TCR beta sequencing.	Optional tumor biopsy		Cycle 3 Day 1 +/- 7 days	Adaptive Biotechnologies ¹ .
TCR beta sequencing.	PBMC	EDTA, 5 ml	See Study Calendar 3.5	Adaptive Biotechnologies ¹

¹ [name], Adaptive Biotechnologies, [name] [contact]. Coded linked samples without key will be sent to Adaptive Biotechnologies.

² Blood samples will initially be sent to the [name] laboratory for barcoding and storage.

5.2 NCI CORRELATIVE STUDIES

5.2.1 Immune monitoring

- We will analyze PBMC for quantitative and functional changes of effector cells as well as analyze sera for cytokines and chemokines. The effect on (i) CD4 T cell number and activity, (ii) CD8 T cell number and activity, (iii) NK cell number and activity, (iv) Treg number, (vi) MDSC: frequency + functional assay, (vii) selected cytokines in serum, and (viii) the detection of tumor-associated antigens using tetramer assay.
- Patients will undergo blood sampling (c.120mls blood) on the time points outlined in the Study Calendar [3.5](#). 12 purple EDTA tubes will be used. Blood will initially be sent to the [name] laboratory for barcoding and processing. On certain occasions, the blood may also be brought to the [name] lab for processing and analysis.
- Specimens will be labeled with the study identifier only and will be shipped to the address above, either on dry ice or at ambient temperatures as required by the type of sample to be analyzed.

5.2.2 Tumor Biopsy

An optional tumor biopsy will be performed at baseline for analysis of PD-L1 expression as well as other factors such as immune infiltration. We will also attempt an optional CT guided biopsy at a subsequent timepoint (after 6 weeks) if the patient is willing and the procedure can be performed safely. Tumor Tissue will be processed by the Department of Pathology, NCI, NIH ([name]). Two core biopsies will be attempted. For each specimen obtained the core will be divided in two parts for Surgical Pathology and frozen preservation. If for some reason only one core is able to be obtained, the core will be divided, with half submitted to Surgical Pathology and half used for PD studies.

1) Formalin-fixed.

- i. The half fixed in 10% formalin will be submitted to Surgical Pathology, CCR/NCI ([name]).
- ii. The specimens will have routine H&E stains made as well as 5 additional unstained sections.

2) Frozen-preservation

- i. Two 1.5 ml cryogenic vials (obtained from [name] lab) will be labeled with the patient's name, accession number (HP#) and date using a waterproof sharpie.
- ii. The isotherm flask ([name] lab) will be filled with liquid nitrogen on the morning of the procedure and will be available together with the cryogenic vials when radiology page the contact person to collect the specimens.
- iii. Once the biopsy is ready, the half-core to be cryopreserved will be transferred into an empty 1.5-mL cryogenic vial with the use of sterile, pre-chilled (in dry ice) disposable tweezers.
- iv. The vial with specimen will be immediately dropped into liquid nitrogen contained in an isotherm flask.
- v. The frozen half will be transferred in the isotherm flask to the protocol-specified location for that particular analysis.

5.2.3 Tumor tissue analysis

Tumor samples from biopsies will be send to the pathology for cancer evaluation, only leftover samples will be used for research.

(i) IHC will be performed on tumor tissue for assessment of immune cell infiltration (e.g. CD3+ CD4/8 cells etc.) as well as other surface markers such as PD-L1.

(ii) Tumor samples will also be used for Nanostring analysis (nCounterPan Cancer Immunology Profile) and TCR beta sequencing. For TCR (cell receptor) gene usage may be quantitated in samples using conventional sequencing techniques of the T cell receptor variable region of the beta chain as is specified in Material Transfer Agreement between NCI and Adaptive Biotechnologies. Fewer than 100 genes will be analyzed. For TCR Beta Sequencing the NCI Thoracic and GI Oncology Branch will release coded tumor and PBMC samples collected in association with this protocol to: [name], Adaptive Biotechnologies, [name] [contact].

5.3 SAMPLE STORAGE, TRACKING AND DISPOSITION

Samples will be ordered in CRIS Screens and tracked through a Clinical Trial Data Management system. Should a CRIS screen not be available, the CRIS downtime procedures will be followed. All samples will be sent to Blood Processing Core (BPC) for processing and storage until they are distributed to [name] lab sample analysis as described in the protocol. Samples will not be sent outside NIH without appropriate approvals and/or agreements, if required.

5.3.1.2 Sample Data Collection

All samples sent to the Blood Processing Core (BPC) will be barcoded, with data entered and stored in the LABrador (aka LabSamples) utilized by the BPC. This is a secure program, with access to LABrador limited to defined [name] lab personnel, who are issued individual user accounts. Installation of LABrador is limited to computers specified by [name]. These computers all have a password restricted login screen.

LABrador creates a unique barcode ID for every sample and sample box, which cannot be traced back to patients without LABrador access. The data recorded for each sample includes the patient ID, name, trial name/protocol number, time drawn, cycle time point, dose, material type, as well as box and freezer location. Patient demographics associated with the clinical center patient number are provided in the system. For each sample, there are notes associated with the processing method (delay in sample processing, storage conditions on the ward, etc.).

Sample bar-codes are linked to patient demographics and limited clinical information. This information will only be provided to investigators listed on this protocol, via registered use of the LABrador. It is critical that the sample remains linked to patient information such as race, age, dates of diagnosis and death, and histological information about the tumor, in order to correlate genotype with these variables

5.3.1.3 Sample Storage

Barcoded samples are stored in barcoded boxes in a locked freezer at either -20 or -80°C according to stability requirements. These freezers are located onsite in the BPC and offsite at NCI Frederick Central Repository Services in Frederick, MD. Visitors to the laboratory are required to be accompanied by laboratory staff at all times.

Access to stored clinical samples is restricted. Samples will be stored until requested by a researcher named on the protocol. All requests are monitored and tracked in LABrador. All researchers are required to sign a form stating that the samples are only to be used for research purposes associated with this trial (as per the IRB approved protocol) and that any unused

samples must be returned to the BPC. It is the responsibility of the NCI Principal Investigator to ensure that the samples requested are being used in a manner consistent with NIH Intramural IRB approval.

Following completion of this study, samples will remain in storage as detailed above. Access to these samples will only be granted following NIH Intramural IRB approval of an additional protocol, granting the rights to use the material.

If, at any time, a patient withdraws from the study and does not wish for their existing samples to be utilized, the individual must provide a written request. Following receipt of this request, the samples will be destroyed (or returned to the patient, if so requested).

The PI will record any loss or unanticipated destruction of samples as a deviation. Reports will be made per the requirements of section [7.2](#).

5.3.2 Procedures for Storage of Tissue Specimens in the Laboratory of Pathology

Tissues designated for clinical diagnostics are transported to the Laboratory of Pathology (LP) where they are examined grossly and relevant portions are fixed, embedded in paraffin and sectioned and stained for diagnostic interpretation. Unutilized excess tissues are stored for up to three months, in accordance with College of American Pathologists/Joint Commission on Accreditation of Healthcare Organizations (CAP/JCAHO) guidelines, and then discarded. Following completion of the diagnostic workup, the slides and tissue blocks are stored indefinitely in the LP's clinical archives. All specimens are catalogued and retrieved utilizing the clinical laboratory information systems, in accordance with CAP/JCAHO regulations. The use of any stored specimens for research purposes is only allowed when the appropriate IRB approval has been obtained. In some cases, this approval has been obtained via the original protocol on which the patient was enrolled.

5.3.3 Procedures for storage of specimens in the Laboratory of [name]

Patient samples, collected for the purpose of research under IRB approved protocols where [name] is Principal Investigator, may be archived in the [name] laboratory. All data associated with archived clinical research samples is entered into the web-based NCI Labmatrix database, centralized system with access controlled via centralized login. Access to this database is limited to [name] research staff, requiring individual login and password. All staff in the [name] laboratory have received annually updated NIH/CIT training and maintain standards of computer security.

The data recorded for each sample may include the patient ID, trial name/protocol number, date drawn/collected, treatment cycle/post-transplant time point, cell source (e.g. peripheral blood, marrow, tissue) as well as box and freezer location. All received samples will receive a unique bar code number, which will be added to the sample NCI Labmatrix database.

Samples are stored in freezers at -80°C (sera, plasma, tissue samples) or under liquid nitrogen (cells), according to stability requirements. These freezers are located onsite at the [name] laboratory. Access to samples from a protocol for research purposes will be by permission of the Principal Investigator.

Contact information:

[name]

[name]

[contact]

E-mail: [contact]

5.3.4 Protocol Completion/Sample Destruction

All specimens obtained in the protocol are used as defined in the protocol. Any specimens that are remaining at the completion of the protocol will be stored in the conditions described in sections above. The study will remain open so long as sample or data analysis continues. Samples from consenting subjects will be stored until they are no longer of scientific value or if a subject withdraws consent for their continued use, at which time they will be destroyed.

If the patient withdraws consent the participant's data will be excluded from future distributions, but data that have already been distributed for approved research use will not be able to be retrieved.

The PI will record any loss or unanticipated destruction of samples as a deviation. Reports will be made per the requirements of section [7.2](#).

5.4 SAMPLES FOR GENETIC/GENOMIC ANALYSIS

TCR (cell receptor) gene usage may be quantitated in samples using conventional sequencing techniques of the T cell receptor variable region of the beta chain. Fewer than 100 genes will be analyzed. For TCR Beta Sequencing the NCI Thoracic and GI Oncology Branch will release coded tumor and PBMC samples to Adaptive Biotechnologies.

5.4.1 Privacy and Confidentiality of medical information/biological specimens

Fresh tumor and blood samples will be stored in a minus 80-degree freezer. Initially the samples of each patient will be sent to [name] lab [\(5.3.1\)](#). At no time will patient's names be used on the blood and tissue samples. The molecular studies will be performed at the Adaptive Biotechnologies, [name] [contact]. Subject's genetic data will be deposited in a database such as dbGaP. Although there is controlled access to such a database, such a submission carries theoretical risks of revealing the identity of the subject. This is discussed in the consent.

5.4.2 Management of Results

There are not going to be incidental findings in this study and the results of molecular studies will not be communicated to the patient.

6 DATA COLLECTION AND EVALUATION

6.1 DATA COLLECTION

The PI will be responsible for overseeing entry of data into an in-house password protected electronic system (C3D) and Labmatrix ensuring data accuracy, consistency and timeliness. The principal investigator, associate investigators/research nurses and/or a contracted data manager will assist with the data management efforts. All data obtained during the conduct of the protocol will be kept in secure network drives or in approved alternative sites that comply with NIH security standards. Primary and final analyzed data will have identifiers so that research data can be attributed to an individual human subject participant.

All adverse events, including clinically significant abnormal findings on laboratory evaluations, regardless of severity, will be followed until return to baseline or stabilization of event.

Document AEs from the first study intervention, Study Day 1 of Cycle 1 through 30 days after the subject received the last study drug administration. Beyond 30 days after the last intervention, only adverse events which are serious and related to the study intervention need to be recorded.

An abnormal laboratory value will be recorded in the database as an AE **only** if the laboratory abnormality is characterized by any of the following:

- Results in discontinuation from the study
- Is associated with clinical signs or symptoms
- Requires treatment or any other therapeutic intervention
- Is associated with death or another serious adverse event, including hospitalization.
- Is judged by the Investigator to be of significant clinical impact
- If any abnormal laboratory result is considered clinically significant, the investigator will provide details about the action taken with respect to the test drug and about the patient's outcome.

Grade 1 adverse events will not be recorded.

End of study procedures: Data will be stored according to HHS, FDA regulations and NIH Intramural Records Retention Schedule as applicable.

Loss or destruction of data: Should we become aware that a major breach in our plan to protect subject confidentiality and trial data has occurred, this will be reported expeditiously per requirements in section [7.2.1](#).

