2.4 BASELINE EVALUATION

Tests done at screening do not need to be repeated on baseline if performed in designated time frame.

Within 28 days prior to first dose:

- CT or PET of chest, abdomen and pelvis (or MRI abdomen)
- Electrocardiogram
- HLA phenotype (any time prior to first dose)
- Optional tumor biopsy for research

Within 7 days prior to first dose:

- History and physical exam with vital signs

Within 72 hours prior to first dose:

[figure not shown]
- Serum or urine pregnancy test for female participants of childbearing age (in the absence of prior hysterectomy).

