6.3.1 Definitions

Evaluable for toxicity: All patients will be evaluable for toxicity from the time of their first treatment with pembrolizumab.

Evaluable for objective response: Only those patients who have measurable disease present at baseline, have received at least one cycle of therapy, and have had their disease re-evaluated will be considered evaluable for response. These patients will have their response classified according to the definitions stated below. (Note: Patients who exhibit objective disease progression prior to the end of cycle 1 will also be considered evaluable.)

Evaluable Non-Target Disease Response: Patients who have lesions present at baseline that are evaluable but do not meet the definitions of measurable disease, have received at least one cycle of therapy, and have had their disease re-evaluated will be considered evaluable for non-target disease. The response assessment is based on the presence, absence, or unequivocal progression of the lesions.

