10.4 EVALUATION OF BENEFITS AND RISKS/DISCOMFORTS FOR ALL PARTICIPANTS

10.4.1 Risk of Optional Biopsy

All care will be taken to minimize risks that may be incurred by tumor sampling. However, there are procedure-related risks (such as bleeding, infection and visceral injury) that will be explained fully during informed consent.

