10.4.2 Risks of exposure to ionizing radiation

This research study involves two CT guided biopsies collected for research purposes only. Subjects undergoing two optional biopsy collections will be exposed to 1.5 rem. This amount of radiation is below the guideline of 5 rem per year allowed for adult research subjects by the NIH Radiation Safety Committee.

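### Adverse event recording starts at Cycle 1 Day 1, so complications of the optional baseline research biopsy that begin before the first dose need not be recorded

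*Combined protocol and SAP*

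**What the plan says.** Section 6.1 sets the start of the recording window: "Document AEs from the first study intervention, Study Day 1 of Cycle 1". The window closes 30 days after the last dose of study drug. After that, only serious events related to the study intervention need be recorded. Grade 1 events are not recorded at all.

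Two other places agree on the start. Section 6.3.1 states: "All patients will be evaluable for toxicity from the time of their first treatment with pembrolizumab". In the study calendar (3.5), adverse event evaluation is marked for Cycles 1-6, Cycle 7 to progression and end of treatment. The Screening and Baseline columns are blank.

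Section 2.4 lists "Optional tumor biopsy for research" among the items due "Within 28 days prior to first dose", and the calendar marks the optional biopsy at Baseline. Section 5.2.2 gives its purpose: "An optional tumor biopsy will be performed at baseline for analysis of PD-L1 expression as well as other factors such as immune infiltration". A second optional biopsy falls on Cycle 3 Day 1, plus or minus 7 days. Section 10.4.2 says of the pair: "This research study involves two CT guided biopsies collected for research purposes only". On the hazards, 10.4.1 says that "there are procedure-related risks (such as bleeding, infection and visceral injury").

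Section 8 addresses safety, tolerability and feasibility by tabulating adverse events by CTCAE grade and reporting them descriptively.

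**The concern.** Section 6.1 treats the first study intervention and Cycle 1 Day 1 as the same moment. For a patient who accepts the baseline biopsy they are not: the protocol has already carried out an invasive procedure. If that procedure causes a bleed, an infection or an organ injury before dosing, no provision requires an adverse event entry.

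At stake is the completeness of the trial's record of harm. The procedure is optional and serves the correlative work, and the protocol itself names what can go wrong. As written, complications of the on-treatment biopsy are collected and pre-dose complications of the baseline biopsy are not. The recorded experience then comes mainly from patients who were still on study and willing at about week 6. A patient whose complication prevented dosing would not be evaluable for toxicity under 6.3.1.

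**Working it through.** The plan gives no figure to reproduce on this point. The check compares timings, then uses a short calculation for scale.

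**Timings side by side**

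| Item | Timing | Source |
|---|---|---|
| Optional baseline research biopsy | Up to 28 days before first dose | 2.4, 5.2.2, calendar |
| Start of adverse event documentation | Cycle 1 Day 1 | 6.1 |
| Start of toxicity evaluability | First pembrolizumab dose | 6.3.1 |
| First scheduled adverse event evaluation | Cycles 1-6 column | 3.5 |
| Optional on-treatment biopsy | Cycle 3 Day 1 ± 7 days | 3.5, 5.1 |

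The gap runs from the baseline biopsy to Cycle 1 Day 1, at most 28 days. The Cycle 3 biopsy lies wholly inside the window. No provision starts adverse event or serious adverse event recording at consent or at the biopsy.

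Could the first study intervention in 6.1 mean the biopsy? The sentence itself equates it with Cycle 1 Day 1. The passage also closes the window at the last study drug administration and then calls that point the last intervention, so the word is used there for drug. If the biopsy were meant, 6.1 would contradict its own day, 6.3.1 and the calendar.

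**Scale**

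Let m be the number of patients biopsied at baseline and q the chance of a complication per biopsy. Then P(at least one) = 1 − (1 − q)^m. The accrual ceiling in Section 8 gives m ≤ 19. Neither q nor uptake is stated, so q = 1%, 2% and 5% and m = 10 are assumptions.

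| Assumed q | m = 10 | m = 19 |
|---|---|---|
| 1% | 1 − 0.99^10 = 9.6% | 1 − 0.99^19 = 17.4% |
| 2% | 1 − 0.98^10 = 18.3% | 1 − 0.98^19 = 31.9% |
| 5% | 1 − 0.95^10 = 40.1% | 1 − 0.95^19 = 62.3% |

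These are chances that a complication occurs at all. If a fraction f of complications begins before Cycle 1 Day 1, the chance that at least one falls in the gap is 1 − (1 − fq)^m, which cannot exceed the tabulated value. The biopsy may be done shortly before dosing, so f may be well below 1.

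**The case against.** The strongest reply is that the window suits the objective. The secondary safety objective concerns pembrolizumab with CAPOX, and an event before any study drug is not toxicity of that regimen. That stands: such events should not enter the drug-toxicity denominator. It does not explain why harm from a research procedure should have no place in the adverse event record, particularly when a complication of the second biopsy does.

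A second reply is that serious events have other routes. Section 7.3 sends deaths within 30 days of a research intervention, other than those due to progressive disease, to the Clinical Director. Section 7.2.1 refers to an NIH reporting policy whose text is not in the documents. Section 7.5.2 commits the investigator to best efforts to report other serious adverse events to the collaborator, whether or not related to pembrolizumab, and does not tie that sentence to first dose. This also stands in part: a serious complication need not go unseen. But these are notification routes. They do not place an event in the Section 8 tabulation, and non-serious Grade 2 events may reach none of them.

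Third, the purpose of the biopsy is less clear-cut than 10.4.2 suggests. Section 5.2.3 sends biopsy tissue to pathology for cancer evaluation, with only leftover tissue used for research. Section 2.2 places screening procedures under a separate protocol and provides for a diagnostic biopsy when no tumor sample exists. That qualifies the research-only description. It does not remove the research biopsy that 2.4 lists under this protocol.

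A reader might also infer that a patient lost to a biopsy complication disappears from the feasibility result. The documents do not support this. They define no feasibility denominator, Section 8 counts patients enrolled and allows for unevaluable ones, and 3.6.3 requires notice to Central Registration when a subject leaves therapy or study. Nor does the Section 10.4 risk assessment rest on the biopsy alone: it also covers radiation, blood draws and drug side effects.

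**Conclusion.** The point holds in a limited form. Three provisions start safety recording at first dosing, and one protocol procedure with named risks precedes it. Following the rule leaves out complications of the baseline biopsy that begin before Cycle 1 Day 1, in patients who accept the biopsy.

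It would be too strong to say that all complications of up to 19 baseline biopsies fall outside the window. The biopsy is optional, uptake is not stated, and a complication that begins after the first dose is recorded. The documents also have no rule that makes an unresolved complication a baseline condition on Day 1; that would be inference. The probabilities of 10% to 40% (10 biopsied) and 17% to 62% (19 biopsied) rest on assumed rates of 1% to 5% and are upper bounds on the chance of a missed event.

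The 5-month PFS endpoint, the two-stage decision rule and the on-treatment toxicity analysis do not change. The matter is completeness of safety recording. It is worth correcting because the correction is cheap.

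**What to change.** - In 6.1, require recording of adverse events attributable to a research procedure from the start of the first such procedure, expressly including the baseline biopsy. Keep all-cause recording from Cycle 1 Day 1.
- In the study calendar, mark adverse event evaluation at Baseline for patients who are biopsied.
- In 6.3.1 and Section 8, report biopsy complications separately from drug toxicity, with all patients biopsied as the denominator, dosed or not. The drug-toxicity population stays as it is.

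The cost is a few sentences, one calendar entry and a little extra data entry for patients who accept the baseline biopsy. No visit, procedure or clinical rule changes.
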